**15 March 2026**

## **Summary of Changes from Previous Version:**

Affected Section(s)	Summary of Revisions Made	Rationale
1.2, 5.2	Added exclusion criteria	Version 1.0 did not exclude examinations for which thyroid nodules were known from prior PET reports (these nodules are known and thus not incidental)
6.3	Updated mortality data source	Between Version 1.0 and this Version 1.1, we added collaborators with expanded access to death records, which will improve accuracy of the mortality outcome
6.3	Added citation	Rationale for 2-year criteria for secondary analyses
7	Updated model covariates related to disease status	Between Version 1.0 and this Version 1.1, we updated our LLM tool to more accurately extract disease status from PET reports, this update reflects the updated LLM

## STATEMENT OF COMPLIANCE

The emulated target trial will be carried out in accordance with International Conference on Harmonisation Good Clinical Practice (ICH GCP) and the following:

- United States (US) Code of Federal Regulations (CFR) applicable to clinical studies (45 CFR Part 46, 21 CFR Part 50, 21 CFR Part 56, 21 CFR Part 312, and/or 21 CFR Part 812)

National Institutes of Health (NIH)-funded investigators and clinical trial site staff who are responsible for the conduct, management, or oversight of NIH-funded clinical trials have completed Human Subjects Protection and ICH GCP Training.

This study has been exempted by the Mass General Brigham Institutional Review Board (IRB) for review and approval. The IRB protocol number is: 2024P002073.

## 1 PROTOCOL SUMMARY

### 1.1 SYNOPSIS

Title:	Mortality Benefit of Ultrasound for Incidental Thyroid Nodules Identified with PET Imaging: A Non-Inferiority Emulated Target Trial
Study Hypothesis:	We hypothesize that all-cause mortality in patients with an incidental thyroid nodule on PET-CT who did not have thyroid ultrasound within 3 months is no worse than 5% higher than those who did have ultrasound.
Outcome Measures:	Primary Outcome: All-cause mortality. Secondary Outcomes: Numbers of thyroid cancer diagnoses, thyroid ultrasounds, thyroid biopsies, and thyroid surgeries Exploratory Outcomes: Types of thyroid cancer diagnoses
Study Population:	All patients age 18-years and older with incidental thyroid nodule on PET-CT performed between 1/1/2015 and 12/31/2021.
Sites/Facilities:	Mass General Brigham healthcare system including Massachusetts General Hospital, Brigham and Women's Hospital, Mass Eye and Ear, and associated community sites.
Exposure:	Thyroid ultrasound evaluation within 3-months of PET-CT

### 1.2 TARGET VS. EMULATED TRIAL TABLE

	Target Clinical Trial	Observational Emulation
Design	Non-inferiority randomized controlled trial	Retrospective non-inferiority cohort study
Aim	Assess whether all-cause mortality in patients with an incidental thyroid nodule on PET-CT who did	Same

	not have thyroid ultrasound within 3 months is no worse than 5% higher than those who did have ultrasound	
Inclusion	Thyroid nodule on PET-CT Age 18 or older Clinic note within 36-months before the PET-CT	Same, with PET-CT scans between 1/1/2015 to 12/31/2021
Exclusion	Prior PET reported thyroid nodule Thyroid ultrasound in prior 3 years Prior thyroid cancer diagnosis	Same
Treatment Strategies	(1) Thyroid ultrasound ordered to be performed within 3 months (2) No thyroid ultrasound ordered	(1) Thyroid ultrasound performed within 3 months (2) No thyroid ultrasound performed within 3 months
Treatment Assignment	Randomized to treatment strategy	Non-randomized to treatment strategy. Randomization emulated via cloning patients in both arms.
Treatment Implementation	3-month grace period	3-month grace period
Outcome	All-cause mortality	Same
Type of Outcome	Failure time	Same
Follow-up Start	PET-CT date, equivalent to treatment assignment	PET-CT date, not equivalent to treatment assignment
Follow-up End	Earliest of death, 7-years from follow-up start, or study end	Same
Censoring	Administrative censoring	Administrative censoring Artificial censoring of clones
Causal Contrast	Intention to treat and per protocol	Per protocol effect only
Non-Inferiority Margin	5%	Same
Statistical Analysis	Non-inferiority intention to treat analysis that consists of comparing probability of mortality between treatment groups at 7 years.	Non-inferiority analysis using clone-censor-weight strategy: 1. Each subject is cloned at study

	
Kaplan-Meier to estimate probability of mortality in each arm
 
Construct a 95% confidence interval for the absolute difference between the two arms, <math>\Delta_{RD}</math>
 
Taking the type I error rate, alpha, to be 0.05, non-inferiority is concluded if the upper limit of a two-sided 90% = 100(1-2alpha)% confidence interval for <math>\Delta_{RD}</math> is less than the prespecified margin.
	
baseline; one clone assigned to each treatment strategy.
 
2. Person-time for each clones is censored when their observed treatment strategy is non-adherent. That is, clones assigned to undergo thyroid ultrasound within 3 months are censored at 3 months of follow-up if no ultrasound is performed. Similarly, clones assigned to not undergo an ultrasound within 3 months are censored at the time an ultrasound is performed.
 
3. A pooled logistic regression model is fit for the (conditional) probability of adherence, adjusting for a priori specified baseline factors that predict adherence.
 
4. A marginal structural pooled logistic regression model is fit to the mortality outcome data, as a function of time and treatment (with interaction), using inverse-probability of censoring weights from step 3.
 
5. Treatment-specific marginal probabilities of all-cause mortality are estimated from the fit in step 4, from which the causal risk difference, <math>\Delta_{RD}</math>, is estimated along with a two-sided 90% = 100(1-2alpha)% confidence interval (constructed via the bootstrap).
 
6. Taking the type I error rate, alpha, to be 0.05, non-inferiority is concluded if the upper limit of a two-sided 90% = 100(1-2alpha)% confidence interval for <math>\Delta_{RD}</math> is less than the prespecified margin.

Secondary Outcomes	
Cumulative over 7-years from PET:
 
Number of thyroid cancers
 
Number of thyroid ultrasounds
	
Cumulative incidence rate over 7-years from PET or to the end of the study period

	Number of thyroid biopsies Number of thyroid surgeries	
Exploratory Analysis	Types of thyroid cancer diagnoses	Same

2 INTRODUCTION

2.1 STUDY RATIONALE

Early pre-symptomatic detection of new or recurrent malignancy is frequently presumed to identify disease at a more treatable stage and, thus, result in better survival than detection due to symptoms. However, evidence often only equivocally supports and frequently contradicts this presumption. Furthermore, most clinical providers incorrectly estimate the harm versus benefit tradeoffs inherent in pre-symptomatic detection strategies. Based on the background information provided in Section 2.2, we hypothesize that all-cause mortality in patients with an incidental thyroid nodule on PET-CT who did not have thyroid ultrasound within 3 months is no worse than 5% higher than those who did have ultrasound.

2.2 BACKGROUND

A recent multi-decade SEER study concluded that overdiagnosis of thyroid cancer is a crucial unresolved public health issue. Overuse of thyroid ultrasound, particularly for clinically unsupported reasons, is a major driver of the overdiagnosis and overtreatment of small non-palpable indolent thyroid cancers. Although evidence is not currently available, it is likely that ultrasound evaluation of incidental thyroid nodules on PET examinations fall into this overuse category, particularly given that the baseline 10-year mortality of patients undergoing PET examinations at our institution are in the range of 30%-50%.

Briefly, thyroid nodules have been detected in up to 65% of people in the United States (U.S.) at autopsy with most autopsy series showing a prevalence of ~50%. However, only 1.1% of people will be diagnosed with thyroid cancer and only 0.4% of all cancer-related deaths are attributable to thyroid cancer. The 5-year survival for all patients with thyroid cancer is 98.6% and 30% of deaths are attributable to anaplastic thyroid carcinoma, which accounts for only 1% of thyroid cancers.

Surgical complication rates in thyroidectomy include a 12% rate of intermediate- to long-term thyroid surgery-specific complications including hypothyroidism, hypoparathyroidism, and hypocalcemia from 1-month to 1-year following surgery in addition to a 6% rate of postoperative fever, hemorrhage, emergency intubation, tracheostomy, pneumonia, and cardiopulmonary and thrombotic complications within 30 days of surgery.

Current American College of Radiology guidelines recommend thyroid ultrasound evaluation of incidental nodules identified on PET with determination for biopsy based on ultrasound characteristics. Based on the TI-RADS lexicon for reporting thyroid ultrasound, 26% of thyroid nodules are recommended for biopsy.

Given the high incidence of thyroid nodules, low rates of thyroid cancer, and low associated mortality, it is likely that workup of incidental thyroid nodules does not impact mortality yet results in patient harm. We thus aim to provide evidence to help understand whether ultrasound evaluation of incidental thyroid nodules on PET examinations contributes to overdiagnosis and overtreatment.

## 2.3 RISK/BENEFIT ASSESSMENT

Known potential risk to subjects is limited to inadvertent breach of confidentiality due to exposure of identified data. This risk will be minimized by following data safety criteria outlined in Section 9. There are likely no direct benefits to subjects, but it is hoped that information gathered from this study may be helpful to the medical care of patients in the future.

## 3 OBJECTIVES AND ENDPOINTS

PRIMARY PURPOSE (OBJECTIVES)	OUTCOME MEASURES	JUSTIFICATION FOR OUTCOME MEASURES
Primary		
Estimate whether all-cause mortality in patients with an incidental thyroid nodule on PET-CT who did not have thyroid ultrasound within 3 months was non-inferior within a 5% margin to those who did have ultrasound.	All-cause mortality	Determined by three thyroid endocrinologists and a head and neck surgeon to be a reasonable timeframe in which thyroid cancers have time to develop and contribute to mortality but not so much that it becomes difficult to separate thyroid cancer-related mortality from other causes.
Secondary		
Estimate whether incidence rates of thyroid cancers, thyroid ultrasounds, thyroid biopsies, and thyroid surgeries are higher in patients with an incidental thyroid nodule on PET-CT who had versus did not have thyroid ultrasound within 3 months.	incidence rate of thyroid cancers, incidence rate of thyroid ultrasounds, incidence rate of thyroid biopsies, incidence rate of thyroid surgeries	Between-group differences in these outcomes will help establish whether the estimated non-inferiority result is clinically meaningful and justifiable due to increased morbidity in those who under further thyroid nodule characterization.
Tertiary/Exploratory		
Explore whether types of thyroid cancer diagnoses are different among patients with an incidental thyroid nodule on PET-CT who had versus did not have thyroid ultrasound within 3 months.	Thyroid cancer subtypes	It is likely that mostly indolent papillary thyroid carcinomas are identified when incidental thyroid nodules are further evaluated.

## 4 STUDY DESIGN

### 4.1 OVERALL DESIGN

We hypothesize that all-cause mortality in patients with an incidental thyroid nodule on PET-CT who did not have thyroid ultrasound (the exposure) within 3 months of the PET-CT is non-inferior within a 5% margin to those who have thyroid ultrasound at 7-years. That is, among patients with an incidental thyroid nodule on PET-CT, mortality is no more than 5% larger (in absolute difference) for those who do not have thyroid ultrasound compared to those who do. We will also report mortality differences at landmark timeframes of 1-year, 3-years, 5-years, and 10-years.

Understanding an expected 30%-50% baseline 10-year mortality rate in patients who undergo PET imaging at our institution, a 5% non-inferiority margin was chosen based on the most conservative proposed margin by 2 thyroid endocrinologists (one did not respond) and a head and neck surgeon (other proposed margins were 7% and 10%). This margin decision was informed by typical margins of 5% to 10% used in non-inferiority trials of medications with outcomes involving mortality and by recent non-inferiority trials of thyroid cancer treatments. The observational nature of this non-inferiority study and absence of prior studies that show effect sizes for the reference make ideal margin point-estimate and fixed-estimate calculations impossible, but our expert panel method is supported as a practical necessity to provide guidance on the fraction of the point estimate of the active comparator that stakeholders are willing to lose at a cost of gaining other advantages (in this case, likely fewer biopsies and surgeries), as in the point-estimate margin calculation method. Given this careful pre-specification of our margin with this panel decision, we will follow published methodology recommendations and consider re-evaluation of the margin based on the secondary benefits seen in the emulated trial or we may conduct the final analysis without reference to a margin. These decisions will be clearly detailed in final manuscripts.

To estimate group differences in mortality, we will conduct a non-inferiority emulated target trial utilizing clone-censor weighting to address potential immortal time bias introduced by the 3-month grace period. We will adjust for all variables labeled as demographic, potential confounder, or mortality risk adjustor in as listed in the Section 7, below.

We will stratify analyses based on baseline disease severity (estimated 5-year relative survival risk) and disease status (progression, lymph node involvement, other sites of metastases).

All subjects will be accrued from the Mass General Brigham healthcare system, which includes two academic medical centers, a specialty head and neck hospital, and multiple community hospitals and numerous community clinics.

## 4.2 SCIENTIFIC RATIONALE FOR STUDY DESIGN

The baseline 10-year mortality of patients undergoing PET examinations at our institution are in the range of 30%-50%. Our interest is in whether, following the detection of a thyroid nodule, doing nothing (i.e. no thyroid ultrasound) results in mortality that is no worse than 5% more than doing something (i.e. thyroid ultrasound). Thus we are using a non-inferiority design. Since performing an ultrasound aligns with ACR recommendations, we've designated the imaged group as the reference group.

## 4.3 END OF STUDY DEFINITION

Mortality data collected up to October 15, 2025. Patients included in the study until they died or until administratively censored.

## 5 STUDY POPULATION

### 5.1 INCLUSION CRITERIA

In order to be included in this study, an individual must meet all of the following criteria:

1. Age  $\geq 18$
2. Thyroid nodule on PET-CT performed 1/1/2015 to 12/31/2021
3. At least one clinical note in the EHR from the 36-month window prior to the PET

Note, there are no restrictions on the indication for the index PET-CT.

### 5.2 EXCLUSION CRITERIA

An individual who meets any of the following criteria will be excluded:

1. Prior PET reported thyroid nodule
2. Thyroid ultrasound listed in the medical record in the prior 3 years
3. Documented history of prior thyroid cancer diagnosis

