### **Explanation**

Inclusion Criteria: 1 = thyroid nodule reported in imaging examination report; 0 = thyroid nodule not reported

age

Inclusion Criteria and Demographic: age in years at time of imaging examination

priorthyroidus

Exclusion Criteria: 1 = thyroid ultrasound performed within 3-years prior to imaging examination; 0 = thyroid US not performed within 3-years prior to imaging examination

priorthyroidcancer

Exclusion Criteria: ICD-10 C73 or ICD-9 193 before PET

NoSustainedCare

Exclusion Criteria: 1 = no provider note within system for 2-years following recommendation

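### Nodules already known from CT or MRI, an older ultrasound, benign biopsy or surgery, or a coded diagnosis still enter as incidental, and no covariate records earlier thyroid work-up

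*Combined protocol and SAP*

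**What the plan says.** Every objective in Section 3 concerns an incidental nodule. Section 5.2, repeated in the exclusion row of the Section 1.2 table, has three exclusions:

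- "Prior PET reported thyroid nodule"
- "Thyroid ultrasound listed in the medical record in the prior 3 years"
- "Documented history of prior thyroid cancer diagnosis"

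The Summary of Changes explains why version 1.1 added the PET exclusion: "these nodules are known and thus not incidental".

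In Section 7 the inclusion variable thyroid_nodule is coded "1 = thyroid nodule reported in imaging examination report; 0 = thyroid nodule not reported". It does not separate a new nodule from a known one. The coded ultrasound exclusion, priorthyroidus, has the same 3-year window: "thyroid ultrasound performed within 3-years prior to imaging examination".

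Step 3 of the emulation (Section 1.2) fits the adherence model on prespecified baseline factors. Section 4.1 takes these from the Section 7 variables labelled demographic, potential confounder or mortality risk adjustor. None of them codes a prior nodule, thyroid ultrasound, thyroid biopsy or benign thyroid surgery. Section 8.4.4 reuses the same weights for the secondary outcomes.

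**The concern.** The plan's reason for removing nodules seen on an earlier PET does not depend on the modality. A nodule reported on CT, scanned five years ago or biopsied as benign is just as well known, yet it stays in the cohort.

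Two separate things follow. First, the cohort is not quite the one named in the title. If ultrasound does help patients with new nodules, patients whose nodule was already cleared have little to gain from it and dilute the contrast. Second, earlier work-up may influence both whether an ultrasound is done within 3 months and what happens afterwards. Every patient is cloned into both arms, so the arms start identical, but censoring separates them by month 3. A weight model without this variable cannot restore the balance.

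The secondary outcomes matter here because Section 3 uses them to judge whether a non-inferiority finding is worth acting on, and Section 4.1 allows the margin to be reconsidered in their light.

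**Working it through.** **1. Trace one patient through the criteria.** Suppose a nodule was scanned and biopsied as benign 4 years before the index PET, and the PET report mentions it as known.

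| Rule | Result |
|---|---|
| Nodule on a prior PET report | Not met |
| Thyroid ultrasound in prior 3 years | Not met (4 years) |
| Prior thyroid cancer | Not met (benign) |
| thyroid_nodule | 1, because the report mentions it |

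The patient enters as an incidental nodule. The cancer exclusion removes earlier work-up that ended in a cancer diagnosis, so the previously evaluated patients who remain are those without one.

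**2. The plan's own figure.** Section 8.2 states at least 75% power for the 5-point margin. It gives no sample size or arm split, so the figure cannot be reproduced. It does imply a standard error if the true difference is zero and one-sided alpha is 0.05 (the 90% interval of Section 1.2):

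SE = 5 / (1.645 + 0.674) = 2.16 points.

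**3. Dilution of the primary outcome.** Let f be the share of the cohort already known and cleared, m the malignancy share among new nodules, and d the 7-year thyroid death risk in those cancers that ultrasound would prevent. The true risk difference in new nodules is m × d, and the shift towards zero is f × m × d. Section 2.2 gives 98.6% 5-year survival, so d = 1.4% is a starting value; it is neither an untreated nor a 7-year figure. The ranges for m (5% to 35%) and f (10% to 50%) are assumptions.

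- True difference: 0.05 × 1.4 = 0.07 to 0.35 × 1.4 = 0.49 points.
- Shift: 0.10 × 0.07 = 0.007 to 0.50 × 0.49 = 0.245 points, about 0.01 to 0.25.
- With harsher d of 5% to 10%: 0.10 × 0.05 × 5 = 0.025 to 0.50 × 0.35 × 10 = 1.75 points.

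**4. Confounding of the primary outcome.** Bias = (difference between arms in the share of known nodules after censoring) × (difference in their all-cause mortality). All inputs are assumed.

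- More known nodules in the no-ultrasound arm by 10 to 30 percentage points, with mortality 1 to 10 points lower: 0.10 × 1 = 0.1 to 0.30 × 10 = 3.0 points towards non-inferiority.
- Same imbalance, with mortality 5 to 10 points higher: 0.10 × 5 = 0.5 to 0.30 × 10 = 3.0 points against it.

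**5. What a favourable bias b would do.** Type I error at the margin = Φ(b/2.16 − 1.645).

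| b (points) | Type I error |
|---|---|
| 0 | 5% |
| 0.2 | 6.0% |
| 0.5 | 7.9% |
| 1.0 | 11.9% |
| 2.0 | 23.7% |

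**6. Secondary outcomes.** Suppose cleared patients have almost no later thyroid events. Then the ultrasound to no-ultrasound rate ratio is multiplied by (1 − k_US)/(1 − k_no), where each k is the share of cleared patients in that arm.

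- Cleared patients only in the no-ultrasound arm, k_no = 10%, 20%, 30%: factors 1/0.9 = 1.11, 1/0.8 = 1.25, 1/0.7 = 1.43.
- Equal shares: factor 1, no distortion.
- k_no = 10%, k_US = 20%: 0.8/0.9 = 0.89, so the contrast shrinks.

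**The case against.** A reader might infer that known nodules gather mainly in the no-ultrasound arm and therefore favour non-inferiority. The documents do not show this. Nothing in them links prior knowledge of a nodule to ultrasound use; a known nodule may be left alone or may prompt a surveillance scan. The endpoint is all-cause mortality in a population whose 10-year mortality the protocol puts at 30% to 50%, and patients with more earlier imaging may be sicker, which would push the other way.

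A reader might also say that at known shares of 10%, 20% and 30% a true excess of 5.6, 6.3 or 7.1 points would read as 5.0, from 5/(1 − k). That holds if the share k is the same in both arms. If known nodules sit only in the no-ultrasound arm, the observed difference is (1 − k) × RD + k × (mortality in known nodules − mortality in the ultrasound arm). With k = 20% and a true difference of 5, this gives 4.0 if the two mortalities are equal, 5.0 or 6.0 if theirs is 5 or 10 points higher, and 3.0 if it is 5 points lower. A 5-point excess through thyroid death is also remote: even at m = 35% it needs d = 5/0.35 = 14.3%, about ten times the 1.4% starting value.

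Nor is the open PET indication an oversight. Section 5.1 says that "there are no restrictions on the indication for the index PET-CT", and Section 7 adjusts in part for neck disease through neck nodes, face lesions, head and neck cancer, prior neck radiation and referring department. None of these records earlier thyroid work-up.

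Finally, the 3-year ultrasound window matches the 36 months in which one clinical note is required. Any-time exclusions would be ascertained unevenly, falling hardest on patients with long in-system records. This stands as a reason not to lead with wider exclusions. It does not explain the missing covariate.

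**Conclusion.** The eligibility gap is real and conflicts with the plan's own reason for the version 1.1 change. The weights cannot repair it, because earlier thyroid work-up is not among the listed covariates.

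Dilution, if ultrasound has any benefit, acts towards non-inferiority. Through thyroid death alone it is probably small against 5 points: about 0.01 to 0.25 on the protocol's survival figure, and up to 1.75 under the harsher assumptions shown. Confounding of all-cause mortality has no established sign. The thyroid-specific secondary contrasts are more exposed, but only if known nodules are unevenly split by ultrasound use. The share affected and its distribution by arm are not given, so every size here rests on assumed inputs. Confidence in the gap is high; in direction and size it is medium. This is a cheap improvement to make before analysis, and it does not by itself undermine the primary conclusion.

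**What to change.** 1. Add a Section 7 baseline covariate for any documented prior thyroid nodule or work-up, built from nodule or goitre codes, any earlier thyroid ultrasound, biopsy or benign thyroid surgery, and one extra LLM field for index reports that describe the nodule as known or previously evaluated. Include it in the step 3 weight model.
2. Prespecify in Section 8.4 an analysis of the primary and secondary outcomes restricted to patients with no such documentation. Report how many patients are affected, by observed ultrasound use.

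The sponsor may instead make this restriction the main eligibility rule in Sections 1.2 and 5.2, stating the look-back limit.

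The cost is a few code lists, one LLM field and an amendment of the kind already made for prior PET. The restricted cohort will be smaller and less precise, which matters with stated power of only at least 75%. Older history will be incompletely captured, because only one note in the prior 36 months is required; the report should say so.
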